Study Protocol and Statistical Analysis Plan

for

RehabTouch: A Mixed-Reality Gym for Rehabilitating the Hands, Arms, Trunk, and Legs after Stroke

NCT03503617

Document Date: 08/31/2021

Trial Design

This study was a single-site, single-blind randomized controlled trial comparing home-based therapy with RehabTouch to conventional therapy for individuals in the subacute phase of stroke. RehabTouch is a commercial home rehabilitation technology (sold as FitMi® by Flint Rehab) designed to put into practice clinically recommended design features for at-home rehabilitation technology. The study was performed at Rancho Los Amigos National Rehabilitation Center in Downey, CA. Participants were invited for an initial assessment to confirm they met the inclusion criteria and to establish baseline measures. Participants provided informed written consent. Qualifying participants were randomly assigned to either the RehabTouch group or the conventional group. Participants in both groups were instructed to perform self-guided therapy for at least three hours/week for three consecutive weeks. All participants received weekly phone calls from a supervising therapist. After the three-week exercise period, participants returned for an end-of-therapy assessment. The trial was pre-registered on ClinicalTrials.gov (NCT03503617) and approved by the Rancho Research Institute, Inc. Institutional Review Board at Rancho Los Amigos National Rehabilitation Center (IRB #263).

Participants

Inclusion criteria were: experienced one or more strokes between 2 weeks and 4 months prior; baseline UEFM Score >5 and ≤55 out of 66; absence of moderate to severe pain defined as a score of 4 or lower on the 10 point visual-analog pain scale; ability to understand the instructions to operate RehabTouch; and aged 18 to 85 years old, as older age could be a confounding variable. Exclusion criteria were: concurrent severe medical problems that precluded the individual from participating in routine rehabilitation; visual deficits defined as a score >1 on question 3 of the NIH Stroke Scale (NIHSS); severe cognitive deficits or apraxia defined as a score >0 on questions 1a and 1c of the NIHSS; severe neglect defined as a score >1 on question 11 of the NIHSS; severe aphasia defined as a score >1 on question 9 of the NIHSS; and enrollment in other therapy studies. Recruitment aimed to balance the age, ethnicity, and gender of the study participants to be representative of Los Angeles County in California, USA. All participants provided informed consent.

Using an estimated effect size of 1.05 based on long-term follow-up data from a previous arm training study during subacute stroke, [1] power analysis established that 21 participants in each group would provide a 90% chance of detecting a significant difference between RehabTouch and conventional therapy at the 0.05 significance level (two-tailed t-test). To account for 20% dropout, the target sample size was n = 25 participants in each group.

Adaptive randomization was used to ensure matched levels of impairment between the RehabTouch and conventional therapy groups. Specifically, subjects were stratified by their UEFM Score into three levels (i.e. 5-22, 23-39, 40-55) and then randomized by alternating block allocation.[2]

Intervention

Participants randomized to the RehabTouch group were given a RehabTouch system with the custom 10" touchscreen tablet. They received 30 minutes of training on how to set up and use the RehabTouch system. They were instructed to spend most of their time performing upper extremity exercises, but access to the trunk and leg exercises in the RehabTouch software was not disabled.

Participants randomized to the conventional therapy group were given a booklet of paper exercises that were selected from the same library of 40 exercises available in the RehabTouch software.

For both groups, a supervising rehabilitation therapist selected the exercises for each participant based on their specific impairments. All participants received 30 minutes of training from the therapist on how to perform the selected exercises correctly.

After the 3-week exercise period, participants returned for an end-of-therapy assessment. At this assessment, participants returned the RehabTouch system or the sensorized booklet of exercises for data collection. Participants returned one month later for a follow-up assessment.

Outcomes

The primary outcome measure was the change in Upper Extremity Fugl-Meyer (UEFM) score[3] from baseline assessment to one-month follow-up. UEFM was assessed at baseline, end-of-therapy, and one-month follow-up. Secondary measures included the Box and Blocks Test,[4] the 10 Meter Walk Test,[5] the Modified Ashworth Spasticity (MAS) scale[6] for the elbow, wrist, and fingers, and the Visual Analog Pain (VAP) scale for the upper extremity, all of which were assessed at baseline, end-of-therapy, and one-month follow-up. Motor Activity Log (MAL) was measured at end-of-therapy and one-month follow-up to assess self-reported quantity and quality of movement.[7] The European Quality of Life five dimensions, three levels (EQ-5D-3L) and its companion Visual Analog Scale (EQ-VAS) were measured at end-of-therapy and at one-month follow-up to assess overall perceived health state,[8], [9] and the Intrinsic Motivation Inventory (IMI)[10] categories of Interest/Enjoyment, Value/Usefulness, and Effort/Importance were measured at end-of-therapy to assess participants' perceived motivation. These measures are widely used in stroke rehabilitation research and have good sensitivity and reliability. All assessments were performed by a blinded, trained evaluator.

To assess adherence, the RehabTouch software recorded the date, time, and number of repetitions completed for each exercise, and the exercise booklet was placed in a sensorized folder that measured the times at which the participants opened the booklet.

Statistical Methods

Statistical analyses were performed using Matlab R2020 software. Change in UEFM score from baseline assessment to one-month follow-up was compared between the RehabTouch group and conventional therapy group using an unpaired two-tailed t-test. Three participants in the conventional therapy group did not perform their one-month follow-up assessment; one of these did perform the end-of-therapy assessment. For this one participant, the missing one-month follow-up data point was imputed for the primary outcome measure by adding the average change in UEFM score across all participants in the conventional therapy group from end-of-therapy to one-month follow-up to this participant's end-of-therapy UEFM score. All other analyses were performed using only data from participants who completed all three assessments.

MAS scores were grouped by flexion or extension items and summed to obtain lumped MAS extension and flexion values. We quantified items marked with a '+,' with an additional 0.5 points for calculations. EQ-5D-L3 was analyzed following.[8], [9] IMI categories were compared across groups using Wilcoxon rank sum tests. For the secondary outcomes with baseline assessments, differences between groups at baseline and at one-month follow-up were assessed using unpaired, two-tailed t-tests. Within group changes from baseline to end-of-therapy and baseline to one-month follow-up were compared using paired, two-tailed t-tests. For the secondary scores were compared to one-month follow-up scores using paired, two-tailed t-tests.

To assess the ability of RehabTouch to motivate an appropriately high dose of home therapy, we performed a post-hoc exploratory analysis comparing the total number of repetitions that RehabTouch participants completed to a theoretical target dose of 2,700 repetitions. A dose of 2,700 repetitions of UE exercise corresponds to 300 repetitions/hour (5 reps/minute) over 9 hours of exercise, an intensity and duration sufficient to provoke a forelimb rehabilitative effect in a rodent model of stroke.[11]

Certain participants were missing data at one or more time points for the secondary outcomes MAS, VAP and IMI. If a participant's record for a given measure was missing data, that participant was omitted from any analysis for that measure. Thus, for MAS calculations (RehabTouch n=13 and conventional n=8), for VAP analysis (RehabTouch n=12 and conventional n=9), and for IMI analysis (RehabTouch n=13).

Interim Analysis

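### The stated allocation rule, read literally, is a systematic sequence rather than a random one, and no concealment is described; the sequence actually used needs stating and the primary analysis needs an adjusted companion.

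*Combined protocol and SAP*

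**What the plan says.** The document describes allocation in three ways.

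- Trial Design: "Qualifying participants were randomly assigned to either the RehabTouch group or the conventional group". This follows the initial assessment that confirms eligibility.
- Participants: "Adaptive randomization was used to ensure matched levels of impairment".
- Participants, next sentence: patients are split into three UEFM bands and "then randomized by alternating block allocation", with a reference attached.

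It gives no block size, no random step within or between blocks, no source of the sequence, no holder of the list and no concealment procedure.

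Three other statements bear on the point.

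- Trial Design: "This study was a single-site, single-blind randomized controlled trial".
- Outcomes: "All assessments were performed by a blinded, trained evaluator". No one else is said to be blinded.
- Intervention: "For both groups, a supervising rehabilitation therapist selected the exercises for each participant". At least one staff member therefore knew assignments in both arms.

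Statistical Methods compares the primary outcome between groups "using an unpaired two-tailed t-test", with no adjustment for stratum or any other baseline variable.

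**The concern.** The three descriptions are not one method. Stratified blocking with a fixed rule is not adaptive, and alternation is not random. The paragraph that should justify treating the two groups as comparable leaves a reader unable to tell whether chance decided who went where.

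Foreseeable assignments matter because whoever can foresee them may, knowingly or not, influence who is invited, when, and how a borderline candidate is judged. Most eligibility items are numeric, but two need judgement: whether the candidate can understand the device instructions, and whether medical problems preclude routine rehabilitation. Time since stroke may range from 2 weeks to 4 months, so candidates within a UEFM band can differ in expected recovery. A prognostic difference introduced at enrolment would pass straight into the change in UEFM, and the unadjusted t-test has no means of removing it.

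**Working it through.** **Plan's own figure.** The document gives none for predictability. The sample size of 21 per group is not affected by this point; it reproduces (noncentral t power 0.913 at 21 and 0.899 at 20, effect size 1.05, two-sided 0.05).

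**Inputs from the document.** Three strata (Participants); 27 of a planned 50 at the interim analysis, and an efficacy threshold of 0.033 there (Interim Analysis); unpaired two-sided t-test (Statistical Methods).

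**Assumptions.** The block size (2, 4 or 6), equally likely strata and the size of any steering are not in the document.

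**Step 1: strict alternation of individuals within stratum.** Only the first assignment in each of the three strata is unknown.

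- N=27: 24/27 = 89% are foreseeable. Guessing the three first ones at 50%, the share guessed correctly is (24 + 1.5)/27 = 94%.
- N=50: 47/50 = 94% are foreseeable; (47 + 1.5)/50 = 97% are guessed correctly.

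**Step 2: fixed permuted blocks.** In a block of size 2m, an assignment is certain once one arm has used its m places. Counting such assignments over all equally likely blocks:

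| Block size | Possible blocks | Certain assignments, total | Mean per block | Share |
|---|---|---|---|---|
| 2 | 2 | 2 | 1.00 | 50% |
| 4 | 6 | 8 | 1.33 | 33% |
| 6 | 20 | 30 | 1.50 | 25% |

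The share is 1/(m+1). It applies to someone who knows the stratum, the block size and the position in the block.

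**Step 3: what steering would do.** In a simulation of 4,000 trials per setting with no true treatment effect, each patient's expected outcome was moved by 0.25 SD towards the arm guessed (the opposite of the last assignment under alternation, otherwise the arm with fewer patients so far in that stratum). Rejection rates of the t-test at 0.05:

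| Scheme | Guessed correctly, N=27 | No steering, N=27 | 0.25 SD, N=27 | 0.25 SD, N=50 |
|---|---|---|---|---|
| Strict alternation | 94% | 5.1% | 19.6% | 37.2% |
| Blocks of 2 | 74% | 4.9% | 8.2% | 12.5% |
| Blocks of 4 | 69% | 4.8% | 7.1% | 9.8% |
| Blocks of 6 | 66% | 4.8% | 6.0% | 8.5% |
| Simple randomisation | 50% | 5.0% | 5.0% | 5.2% |

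**Step 4: check of the largest N=27 figure.** Under alternation the arms differ by 2 × 0.25 × 24/27 = 0.444 SD. With 14 v 13 (assumed split), the noncentrality is 0.444/√(1/14 + 1/13) = 1.154. On 25 degrees of freedom the two-sided rejection rate is 19.9% at 0.05, in line with the simulated 19.6%. At the interim threshold of 0.033 the same shift gives 15.2%.

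**The case against.** The strongest reply is that the key term is undefined. The same sentence says patients were randomized, Trial Design says so too, and the phrase may be loose wording for concealed, randomly permuted blocks. The attached reference might settle it, but the document does not reproduce a definition. This stands, and it is why the conclusion is conditional on what was done.

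Several stronger readings are tempting and the document does not support them.

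- *The last assignment reveals the next.* True only if individuals alternate. If whole blocks alternate, one also needs the position in the block.
- *The supervising therapist could steer enrolment.* That role is described as exercise selection and training. No section gives it screening or enrolment duties.
- *Enrolment was steered, or the result is a false positive.* There is no evidence of either. Assignment follows the baseline assessment, the stratum is known only once UEFM is scored, and a blinded evaluator does the scoring. This narrows the route to bias. It does not close it, because who is invited and when, and the judgement-based criteria, come before assignment.
- *The false-positive rate is a known figure.* Every such rate depends on an assumed amount of steering. Without steering, all the schemes stay near 5%. The rates quoted at 0.05 also overstate the risk for an efficacy decision at the interim, where the threshold is 0.033.

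**Conclusion.** The point holds in a limited form. The allocation paragraph contradicts itself, its literal reading is a systematic sequence, and no concealment is described at a single site where only the evaluator is stated to be blinded.

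The degree of predictability depends on the reading: all but the first assignment in each stratum under alternation of individuals, and 50%, 33% or 25% known with certainty under fixed permuted blocks of 2, 4 or 6. The consequence for error rates is potential, not shown. At N=27 and the 0.05 level it would be about 20% under alternation and 7% to 8% under blocks of 4 or 2, if each foreseen assignment were steered by an assumed 0.25 SD.

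It should be corrected, because the primary comparison rests on this paragraph. A reader may infer that the trial was not randomised; the document leaves that open and does not establish it.

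**What to change.** The document is written in the past tense and recruitment was halted in March 2020, so most of the remedy is reporting and analysis.

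1. Replace the allocation sentences with what was done: how the sequence was generated, the block size or sizes, who held the list, and when each assignment was released. Drop *adaptive*.
2. Add a sensitivity analysis of the primary outcome: change in UEFM regressed on group, baseline UEFM (or stratum) and time since stroke. Label it as added after the fact.
3. If the sequence alternated, describe the trial as quasi-randomised, report this as a limitation and word the conclusion accordingly.
4. For any further enrolment, use computer-generated random permuted blocks within the same three strata. The list should be held by someone who neither enrols nor assesses, with each assignment released only after consent and baseline UEFM are recorded. Concealment is the important part: in the simulation, a random mix of blocks of 2, 4 and 6 was guessed correctly 68% of the time at N=27, against 69% for fixed blocks of 4.

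The cost is small: one rewritten paragraph and one extra model. The two covariates use two degrees of freedom in a sample of about 25 (27 less the two conventional-group patients with neither a follow-up nor an imputed value, if all 27 were randomised). Adjustment removes only differences carried by the measured covariates, so the conclusion may still need more caution.

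### Four secondary outcomes have a baseline that the one-month group comparison ignores, and their change is tested only within each arm

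*Combined protocol and SAP*

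**What the plan says.** The Outcomes section lists Box and Blocks, the 10 Meter Walk Test, MAS and VAP, "all of which were assessed at baseline, end-of-therapy, and one-month follow-up". Each therefore has its own baseline. MAS is analysed as two sums (flexion and extension), so the four measures give five scores.

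Statistical Methods gives these outcomes two kinds of test:

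- Between groups: "differences between groups at baseline and at one-month follow-up were assessed using unpaired, two-tailed t-tests".
- Within groups: "Within group changes from baseline to end-of-therapy and baseline to one-month follow-up were compared using paired, two-tailed t-tests".

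The primary outcome is handled differently: "Change in UEFM score from baseline assessment to one-month follow-up was compared between the RehabTouch group and conventional therapy group". Its baseline enters the group comparison.

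The analysed numbers are given for two of the four measures: "for MAS calculations (RehabTouch n=13 and conventional n=8), for VAP analysis (RehabTouch n=12 and conventional n=9".

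Other secondary outcomes lie outside this point. For IMI, "IMI categories were compared across groups using Wilcoxon rank sum tests", which is a between-group test. The sentence that may govern MAL, EQ-5D-3L and EQ-VAS has lost words as it reads here: "For the secondary scores were compared to one-month follow-up scores using paired, two-tailed t-tests". Nothing is asserted about those three.

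**The concern.** The trial compares two home programmes, so what matters for each secondary outcome is the difference between arms. For these four outcomes that difference is tested once, on raw one-month scores. No covariate and no change score is used, and no between-group comparison is stated at end-of-therapy. The separate baseline t-test can display an imbalance but does not correct for it. Stratification was on UEFM, so it does not bring the other baselines into the analysis.

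Change is tested only within each arm. Participants enter 2 weeks to 4 months after stroke and both arms exercise, so a significant within-arm change may be natural recovery. Reading one significant arm beside one non-significant arm as a treatment effect is a known trap, and it is worse when the arms are small and unequal. With 21 analysed participants for MAS and for VAP, a baseline already collected should not be left out.

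**Working it through.** **Reading the text.** Could the quoted differences mean differences in change? The same phrase covers baseline, where no change exists, so the plain reading is raw scores. The damaged sentence describes a paired test, so its surviving words do not supply a between-group contrast.

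**Inputs.** From the document: MAS 13 v 8, VAP 12 v 9 (N = 21 each) and two-sided alpha 0.05. Assumed: a true difference d = 0.5 SD, and a correlation ρ between baseline and one-month score from 0.3 to 0.9. The document gives no ρ. It states no arm sizes for Box and Blocks or 10 Meter Walk, so no power is computed for them.

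**The plan's own figure.** Its only power calculation is for UEFM. The noncentral t with d = 1.05 gives 91.3% at 21 per group and 89.9% at 20, so 21 is reproduced. No power is stated for the secondary outcomes.

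**Precision, unadjusted.** SE = √(1/n₁ + 1/n₂).

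- MAS: √(1/13 + 1/8) = 0.449 SD; noncentrality 0.5/0.449 = 1.11; 19 df; power 18.5%.
- VAP: √(1/12 + 1/9) = 0.441 SD; noncentrality 0.5/0.441 = 1.13; 19 df; power 19.0%.

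**Precision, adjusted for own baseline.** The SE is multiplied by √(1 − ρ²), with 18 df. Estimating the covariate inflates the variance by a further 1 + 1/(N − 4) = 1 + 1/17 = 1.059.

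| ρ | Variance left, 1 − ρ² | MAS power, without / with that factor | VAP power, without / with that factor |
|---|---|---|---|
| 0.3 | 0.91 | 19.7% / 18.9% | 20.3% / 19.4% |
| 0.5 | 0.75 | 22.9% / 21.9% | 23.6% / 22.6% |
| 0.7 | 0.51 | 31.4% / 30.0% | 32.4% / 30.9% |
| 0.8 | 0.36 | 41.9% / 40.0% | 43.2% / 41.3% |
| 0.9 | 0.19 | 67.5% / 65.1% | 69.2% / 66.7% |

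A 40,000-run simulation for MAS gives 18.9%, 22.1%, 30.4%, 39.8% and 65.2%, in line with the figures that include the factor. At ρ = 0 it gives 17.5% adjusted against 18.3% raw, a loss of about one point.

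**The same loss seen in one sample.** If the outcome is unrelated to the UEFM strata, the SE of a chance baseline difference is also 0.449 SD (MAS) or 0.441 SD (VAP); it is smaller if related. The raw one-month contrast carries ρ times the imbalance. For MAS, a one-SE imbalance moves it by ρ × 0.449 = 0.13, 0.22, 0.31, 0.36 and 0.40 SD at the five values of ρ.

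**Within-arm tests.** Suppose both arms truly change by the same amount, in SDs of change (assumed). With p₁ and p₂ the paired-t power in each arm, the chance that exactly one is significant is p₁(1 − p₂) + p₂(1 − p₁).

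| True change, both arms | MAS p₁ (n = 13), p₂ (n = 8) | MAS: one arm only | VAP p₁ (n = 12), p₂ (n = 9) | VAP: one arm only |
|---|---|---|---|---|
| 0.3 | 0.169, 0.114 | 0.245 | 0.158, 0.125 | 0.244 |
| 0.5 | 0.382, 0.232 | 0.437 | 0.353, 0.263 | 0.430 |
| 0.8 | 0.754, 0.496 | 0.502 | 0.714, 0.559 | 0.475 |

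The disagreement favours the larger arm. For MAS at 0.8, RehabTouch alone is significant with probability 0.754 × 0.504 = 0.38, and conventional alone with 0.496 × 0.246 = 0.12, although the arms do not differ.

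**Change scores as an alternative.** Their variance relative to raw scores is 2(1 − ρ) = 1.40, 1.00, 0.60, 0.40 and 0.20. They are less precise than the raw test when ρ is below 0.5.

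**The case against.** The strongest reply is that a valid randomised comparison already exists for each outcome at the primary time point, so what is lost is efficiency on secondary outcomes. That stands. After the covariate-estimation factor, MAS power rises only from 18.5% to 18.9% at ρ = 0.3 and 21.9% at ρ = 0.5. A low ρ may well apply to VAP, whose range is restricted at entry to "a score of 4 or lower on the 10 point visual-analog pain scale". Even with adjustment, power is low at most values of ρ.

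It is also fair that the imbalance figures are the same inefficiency viewed conditionally; the two should not be added together.

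The document nowhere says it will infer a treatment effect from one arm being significant and the other not, and with no true change in either arm the disagreement rate is only 9.5%. That stands too. But these are the only tests of change for the four outcomes, and the only tests of any kind stated at end-of-therapy, so the plan offers no other result there.

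MAS sums ordinal grades and VAP is bounded, so a normal-theory model might seem unsafe at 13 v 8. A simulation with rounded, floor-limited scores at those sizes kept the adjusted test's type I error at 4.6% to 5.2%, so this does not block the remedy. The power gains above still assume normal scores.

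End-of-therapy comparisons would add five contrasts. That is a real cost, met by treating them as exploratory estimates.

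**Conclusion.** The concern holds. For Box and Blocks, 10 Meter Walk, MAS and VAP, the plan compares raw one-month scores between arms and tests change only within arms, although each outcome has its own baseline and the primary analysis uses its baseline.

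The harm is to precision and interpretation; the one-month test is not biased over randomisation. The precision lost ranges from negligible at ρ = 0.3 to large at ρ = 0.9, and ρ is unknown. The interpretation problem does not depend on ρ as framed here: under equal true changes of 0.3 to 0.8 SD, the two arms' paired tests disagree in about 24% to 50% of trials. Nothing is quantified for Box and Blocks or 10 Meter Walk. The change is worth making because it is cheap; the primary conclusion does not depend on it.

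**What to change.** For each of the four outcomes (five scores), fit a linear model of the follow-up value on group and the outcome's own baseline. Report the group difference with a 95% CI at one month and also at end-of-therapy. Treat the five end-of-therapy contrasts as exploratory. Prefer this to a between-group test of change, which is worse than the raw test when ρ is below 0.5. Present within-arm changes as description, without using their p-values as evidence of a treatment effect.

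For MAL, EQ-5D-3L and EQ-VAS, restore the incomplete sentence. If it provides only a paired within-arm test, base the treatment comparison on a between-group test. IMI needs no change.

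The cost is a refit on data already collected, one degree of freedom per model, and about one point of power if ρ is near zero. The analyses are described as already done, so the refit must be labelled post hoc and shown beside the tests already reported.

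### No between-group efficacy comparison is stated at end-of-therapy; change over the three treatment weeks is tested only within each arm

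*Combined protocol and SAP*

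**What the plan says.** The Trial Design section describes a "single-site, single-blind randomized controlled trial comparing home-based therapy with RehabTouch to conventional therapy for individuals in the subacute phase of stroke". Both groups were "instructed to perform self-guided therapy for at least three hours/week for three consecutive weeks". Under Participants, eligible patients had "experienced one or more strokes between 2 weeks and 4 months prior".

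Under Outcomes, "UEFM was assessed at baseline, end-of-therapy, and one-month follow-up". Box and Blocks, the 10 Meter Walk, MAS and VAP follow the same three-visit schedule, rated by a blinded evaluator. The primary endpoint is set later than the end of treatment: "The primary outcome measure was the change in Upper Extremity Fugl-Meyer (UEFM) score[3] from baseline assessment to one-month follow-up". The Intervention section gives the interval between the last two visits: "Participants returned one month later for a follow-up assessment".

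The Statistical Methods section then states these efficacy tests:

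- **Primary:** an unpaired t-test between groups on UEFM change from baseline to one month.
- **Secondary outcomes with a baseline, between groups:** "differences between groups at baseline and at one-month follow-up were assessed using unpaired, two-tailed t-tests".
- **Change within each arm:** "Within group changes from baseline to end-of-therapy and baseline to one-month follow-up were compared using paired, two-tailed t-tests".

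The next sentence appears to have lost words. What remains describes another paired comparison with one-month scores. The only between-group test stated on end-of-therapy data is the rank sum test on IMI, which measures motivation and not efficacy. No between-group test is stated for MAL, and EQ-5D is said only to be analysed following two references.

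**The concern.** Randomisation allows a change seen in one arm to be set against the same change in the other. A paired test within one arm does not use it. Its null hypothesis is zero change, which can be false for reasons unrelated to the assigned therapy: natural recovery, usual care, repeated testing or regression to the mean. Natural recovery is a reasonable inference from the entry window of 2 weeks to 4 months after stroke. The documents do not mention it, and the argument does not depend on it alone.

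Two things are at stake. First, paired p-values from arms of unequal size invite a comparison of significance labels, and the larger arm has the advantage even when true change is equal. In the stated MAS and VAP numbers the larger arm is RehabTouch. Second, the system or booklet is handed back at the end-of-therapy visit and the next assessment is a month later. Without an end-of-therapy contrast, the report says nothing about whether a null one-month result followed an early difference that faded.

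**Working it through.** **1. Which contrasts are stated, for outcomes with a baseline**

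| Interval or visit | Between groups | Within group |
|---|---|---|
| Baseline | Yes (secondary outcomes) | n/a |
| Baseline to end-of-therapy | None | Paired t-test |
| One month | Yes (UEFM change; secondary outcomes) | Paired t-test on change from baseline |

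The sentence on within-group change follows one about secondary outcomes, so it may or may not cover UEFM. On either reading, the between-group cell for end-of-therapy is empty.

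**2. The plan's own figure.** The plan gives 21 per group for 90% power at effect size 1.05, two-sided 0.05. The noncentrality is 1.05/√(2/21) = 3.40 and the critical t on 40 df is 2.021, so power is 0.913. At 20 per group it is 0.899. The figure reproduces, and it concerns the between-group comparison, not any paired test.

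**3. Comparing significance labels when there is no treatment difference**

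Inputs from Statistical Methods: MAS 13 vs 8 and VAP 12 vs 9 (RehabTouch vs conventional). Assumption: the same standardised change δ (mean change divided by the SD of change) in both arms. The documents give no value, so a range is shown.

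Power of a paired t-test with n participants: p = P(|T| > t₀.₉₇₅,ₙ₋₁), where T is noncentral t with n−1 df and noncentrality δ√n. The arms are independent, so P(RehabTouch significant, conventional not) = p₁(1 − p₂).

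Worked case, MAS, δ = 0.8:
- n = 13: noncentrality 0.8 × √13 = 2.88, critical value 2.179, p₁ = 0.754
- n = 8: noncentrality 0.8 × √8 = 2.26, critical value 2.365, p₂ = 0.496
- 0.754 × (1 − 0.496) = 0.38

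| δ | MAS p₁ / p₂ | MAS, RehabTouch only | VAP p₁ / p₂ | VAP, RehabTouch only |
|---|---|---|---|---|
| 0.2 | 0.10 / 0.08 | 9% | 0.10 / 0.08 | 9% |
| 0.5 | 0.38 / 0.23 | 29% | 0.35 / 0.26 | 26% |
| 0.8 | 0.75 / 0.50 | 38% | 0.71 / 0.56 | 31% |
| 1.0 | 0.91 / 0.68 | 29% | 0.88 / 0.75 | 22% |
| 1.5 | 0.999 / 0.95 | 5% | 0.997 / 0.97 | 3% |

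Under the same assumption, a between-group t-test of change rejects at its nominal 5%.

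**4. What the missing contrast could show.** Power of an unpaired t-test uses noncentrality d/√(1/n₁ + 1/n₂). At 13 vs 8, √(1/13 + 1/8) = 0.449 and the critical t on 19 df is 2.093. For assumed standardised differences d of 0.5, 0.8 and 1.05, the noncentralities are 1.11, 1.78 and 2.34, and power is 0.18, 0.39 and 0.60. The 95% interval would extend about 2.093 × 0.449 = 0.94 SD either side of the estimate.

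**The case against.** A reader might infer that the trial has no randomised answer on the three-week programme at all. The documents do not support that. The primary analysis is a randomised comparison of UEFM change over an interval that contains the three weeks, and secondary outcomes with a baseline are also compared between groups at one month. Nor would an end-of-therapy contrast give the effect of the programme against no therapy. Both arms exercised, with exercises from the same library, so it would estimate RehabTouch against conventional therapy.

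Other objections carry some weight:

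- *Timing is a design choice.* The effect size comes from long-term follow-up data, and a one-month primary endpoint is consistent with that. This stands. The point concerns secondary inference and leaves the primary alone.
- *The misreading is hypothetical.* Nothing in the plan says paired p-values will be compared across arms or read as efficacy. This stands too: the percentages describe how often a misleading pattern would appear, not the error rate of a stated test.
- *The percentages depend on the assumptions.* The 38% needs a change near 0.8 and the more unequal of the two pairs of arm sizes. The documents support no such change in MAS, which measures spasticity, and the pain criterion at entry limits how far VAP can improve. Hence the range.
- *The added contrast is weak.* At these numbers a null result at both visits would usually remain ambiguous.

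None of these makes a paired test answer a between-group question.

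**Conclusion.** The point holds in a limited form. No between-group efficacy comparison is stated at end-of-therapy, so the immediate effect relative to conventional therapy is not tested, although the data exist in both arms. The paired tests cannot supply it. The sentence that has lost words is unlikely to fill the gap, because its surviving part also describes a paired test; its full content cannot be recovered from the text.

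If true change were equal in both arms, the pattern favouring RehabTouch would appear about 22% to 38% of the time at the MAS and VAP numbers for assumed standardised changes of 0.5 to 1.0, and about 9% or less at 0.2 or 1.5. These figures rest on assumed changes, equal δ in both arms, approximately normal change scores and independent arms. The one-month primary inference is untouched. This is an inexpensive improvement to the secondary analysis.

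**What to change.** Add the between-group difference in baseline to end-of-therapy change, with a 95% confidence interval, for UEFM, Box and Blocks, the 10 Meter Walk, MAS and VAP. State which participants enter each contrast. Label these contrasts post hoc secondary and unadjusted for multiplicity: the document is dated 08/31/2021, is written in the past tense, and already reports missing-data counts and an interim analysis, so they cannot be presented as prespecified.

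Report within-group changes to end-of-therapy and to one month as means with confidence intervals, without p-values, and note that they include any change common to both arms. Restore the missing words in the incomplete sentence on secondary scores.

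The cost is some wording and a few calculations on data already collected. The downside is a handful of extra unadjusted contrasts with low power. The text should therefore lead with the interval and say that a null result would not rule out an early effect.
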